Chronic post-surgical pain – To evaluate for the presence of CPSP, subjects will be asked at 3- and 6-months if they have pain in the surgical site that developed or increased in intensity following the surgery utilizing a checklist based upon the IASP definition of CPSP (Appendix). If they respond affirmatively, BPI pain scores will be collected to assess the intensity and interference associated with the CPSP. In addition, subjects will be asked if they are continuing to use opioids at these timepoints, and if so, daily MEDD calculated for analysis.

2. Group Modifications:

The only group modification with respect to measures is that only those in the intervention group will participate in the survey assessing subject satisfaction with the intervention.

3. Method for Assigning Subjects to Groups:

A randomization scheme will be generated by the study biostatistician and provided to the study coordinator who will assign consecutively enrolled subjects to group.

4. Administration of Surveys and/or Process:

The data collection schedule is described below:

	Baseline (T-4weeks)	Pre-operation (T0)	Post-operation (T = 72hr)	Follow-up (T + 3 and 6 months)
Chronic Pain Intensity (BPI)	X	X		X
Opioid Use (MEDD)	X	X		X
PDMP review	X			X
Pain Catastrophizing (PCS)	X	X		X
Depression & Anxiety symptoms (PROMIS)	X	X		X
CBT use, adherence, satisfaction ^a		X		
Post-operative Pain Severity (72hr VAS)			X	
Post-operative Pain Severity (72hr MEDD)			X	
Chronic post-surgical pain checklist				X

^a subjects in treatment group only

5. Data Management:

Collected data will be entered into the U Penn School of Nursing REDCap (Research Electronic Data Capture) system by trained CITI- and HIPAA-certified research assistants, which is a central and secure resource for data processing and management. As the front-end collection instrument is created, REDCap automatically creates a database designed to store the data that will be recorded from the research. The U Penn School of Nursing has licensed its own version of REDCap that is housed on password protected servers located within a data center inside the School of Nursing firewall, and therefore are afforded the same network protections as other sensitive clinical systems. REDCap was developed specifically around HIPAA-Security guidelines with features such as data encryption and is recommended to Penn researchers by our Office of Human Research.

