Data quality will be monitored by random inspection of the completed datasets by the study coordinator and any problems detected will be discussed with the co-PIs. In addition, the PIs will carefully monitor the data accrual weekly. Data will be entered on an ongoing basis under the direction of the study coordinator, and weekly reports detailing health events, study progress, and data accuracy and completeness will be generated for review by the PIs and co-investigators. Quality assurance activities will be supervised by the study coordinator. Prior to analysis, missing data or discrepancies will be corrected by the project director based on source documents. The study's statistician will analyze the data, using SAS for Windows Version 9.4 statistical software.

Data monitoring of all aspects of this study will proceed in an exacting manner and meet all IRB requirements. Data will be collected by trained research staff using standardized hardcopy and electronic forms and will only be identified with a study ID. Personal identifiers required for follow-up will be linked with the study ID and kept confidential by Drs. [name] and [name] in a secured cabinet. No presentation or publication of the results of this study will refer to the individual participants or present information that would identify any participant. No data will be disclosed to personnel not listed on the study protocol.

6. Subject Follow-up:

Using contact information obtained at the baseline visit, subjects will be contacted via telephone at 3- and 6-months following surgery to determine if CPSP is present utilizing a checklist based upon the IASP definition of CPSP (Appendix). If present, the BPI will be administered, and any opioid use recorded and checked against the PDMP. In addition, the PCS and PROMIS measures will be collected to evaluate the durability of CBT training effects. The sample does not include transient groups, minimizing potential attrition.

STUDY PROCEDURES:

1. Detailed Description:

The study procedures, including all the visits, contacts, and interactions are described sequentially below:

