session before completing it and resume where they left off, and access program resources to manage goals and reminders, log practices, review progress in easy-to-read graphs, read about others' experiences using the skills, and share their own. In addition, they will have access to PAINTrainer for one-month post operatively to reinforce the basic CBT principles; the program also tracks participants' use. Although it is recommended to complete one session per week, in this application patients will be asked to complete 2 sessions per week for four weeks; the developers of the PAINTrainer (consultants [name] and [name]) note that the efficacy of flexible approaches, including shortening of the delivery schedule.

In addition to the PAINTrainer, we will integrate a motivational interviewing (MI) intervention delivered by a trained "coach" across the sessions about (1) the benefits of opioid tapering for post-operative pain control, (2) approaches for safely tapering, (3) identifying and managing withdrawal symptoms patients may experience. Co-PI [name] will provide scripted language and train the study coordinator to effectively deliver this education within the CBT context employing MI techniques, and monitor fidelity to the delivery at regular intervals over the course of the study. The content and tapering guidelines will be based upon the US Department of Veterans Affairs Pain Management Opioid Taper Decision Tool⁵⁵ which provides guidance on dose reduction schedules, over-the-counter medications to treat mild withdrawal symptoms, and resources to manage discomfort or distress. Patients will not be expected to taper completely off opioids during the intervention period, but up to 30% reduction in daily opioid dose is anticipated. For future testing, the MI intervention will be integrated into the platform virtual coach, however it is cost-prohibitive to do so in the current application.

Treatment as usual: Patients scheduled to undergo total joint arthroplasty at the study site are automatically enrolled in a mandatory 4-hour education class delivered by a nurse educator or physical therapist. Utilizing an in-person PowerPoint presentation format, patients are informed about pre-habilitation exercises to do prior to surgery; what to expect the day of surgery; the multimodal analgesia protocol used in the perioperative period; options for anesthesia and analgesia; and the expectation of physical therapy after surgery.

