Pre-operative study session: Immediately prior to the surgical procedure, patients in the experimental group will meet with the study coordinator and baseline assessments will be repeated. In addition, the subject will be interviewed to gain understanding of their perceived ease, burden, satisfaction and likability of the intervention. It is anticipated that this study session will last no longer than 45 minutes. At the completion of the session, use data from the computer-assisted CBT program will be downloaded and recorded.

Post-operative Pain: Post-operative pain intensity and opioid use (converted to MEDD) data will be extracted from the EHR for the first 72 hours post-operatively. If the patient is discharged prior to 72 hours, he or she will be provided a pain diary to record daily pain ratings and opioid use.

Chronic Post-surgical Pain: Subjects will be contacted via telephone at 3- and 6-months following surgery to determine if CPSP is present utilizing a checklist based upon the IASP definition of CPSP (Appendix). If present, the BPI will be administered, and any opioid use recorded and checked against the PDMP. In addition, the PCS and PROMIS measures will be collected to evaluate the durability of CBT training effects.

2. Data Collection:

Data related to 72-hour post-operative pain and opioid use outcomes will be extracted from the EHR and opioid use data will be validated from PDMP entries; all other data will be sourced directly from the subject. These data are not existing at the time of submission of the IRB application. No tissue specimens will be collected or used in this study.

3. Genetic Testing:

Not applicable.

4. Use of Deception:

Not applicable.

5. Statistical Analysis:

Preliminary analysis of all outcome and baseline demographic variables will describe and test for differences in baseline measures between the groups. Adequacy of randomization will be evaluated by tests of differences between the intervention and usual care groups. These baseline comparisons will be based on t-tests or Wilcoxon rank sum tests for continuous variables, depending on the symmetry of the distributions; on logistic regression for

binary or ordinal variables; and on Poisson log-linear regression for count data. If imbalances are found at baseline, then the relevant variables will be treated as confounders in the post study analyses.

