Opioid taper: As a part of the intervention and with the guidance of their trained coach, one-half of the subjects will be encouraged to gradually taper their opioid use in the month prior to surgery. It is possible that in doing so, subjects may experience the uncomfortable symptoms associated with opioid withdrawal. To avoid the emergence of these, subjects will be instructed to taper their dose gradually (no more than 10%/week), and will be provided with information on how to self-manage these symptoms should they arise. In addition, subjects will be instructed to contact their coach should the symptoms become severe, to receive guidance on how to temporarily cease and then restart taper attempts. In that subjects will have been regular users of opioids for at least three months prior to study enrollment, they will have developed a certain degree of physiologic tolerance, offering protection against any respiratory depressant effects during a taper pause.

Breach of Confidentiality: Participation in this study may constitute a social risk to the participant in that others may learn that he or she has chronic pain and is taking opioid medications. Due to the sensitive nature of this information, privacy and confidentiality will be strictly maintained in all aspects of participation. Consent and data collection sessions will take place in private rooms where strict privacy is enforced and all staff are HIPAA certified.

Acute Anxiety or Depressive Symptoms: It is possible that the opioid taper for the intervention group, or the upcoming surgery for both groups may precipitate unanticipated symptoms of acute anxiety or depression. As described below, co-PI [name] is a licensed clinical psychologist with over 40 years' experience in treating patients with chronic pain, will be available to assess and intervene with patients who experience these distressing symptoms during the pre-operative period.

2. Benefits:

The potential benefit for both the participants and broader segments of society is to improve pain outcomes following a very common procedure, TKA, ideally decreasing the severity of post-operative pain experienced and

the development of CPSP. Development of an effective intervention to address the risk factors for poor pain outcomes following TKA can guide clinical practice based upon evidence.

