The Study Coordinator/Coach, TBH, will devote 12 calendar months effort to the study over both years of the project. This individual will come to the project with experience in coordinating human subject clinical research studies and be responsible for enrolling subjects, scheduling study visits, all aspects of data collection, entering study data into REDCap, and engaging in ongoing communication with IRB, study setting and U Penn School of Medicine and Nursing, Department of Anesthesiology and Department of Orthopaedic Surgery. In addition, this individual will receive directed training and monitoring from Co-PI [name] to oversee delivery of the CBT and opioid tapering MI intervention. In this role, this individual will serve as a "coach" to the subjects, contacting them on a weekly basis prior to surgery, educating and motivating them to engage in preoperative opioid reduction.

Participants will be recruited from the nationally renowned Department of Orthopaedic Surgery at PPMC. Center surgeons perform approximately 1800 major TKAs per year, an estimated 20-30% of whom have been taking opioids for at least 3 months for the treatment of a chronic nonmalignant pain condition, resulting in a recruitment pool of 30 to 45 patients per month, providing an adequate source of the necessary 12-13 enrollments per month.

In addition, the facilities and resources are adequate to safely conduct the study. Situated within the Department of Psychiatry is the Center for Studies on Addiction (CSA), where Co-Principal Investigator [name] holds an appointment. A primary mission of the CSA is to continue to advance the cutting edge of knowledge on the nature of addiction and the best ways to treat this disorder. The CSA has, for the past 40 years, been an important

national and international resource for addictions research. The PI ([name]) has conducted large-scale studies on pain and opioid use disorders and suicide and has an established relationship at the primary recruitment site.

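### The coordinator who coaches the intervention arm is also given responsibility for data collection, and no independent or blinded assessor is specified for the self-reported outcomes, including the primary one

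*Combined protocol and SAP*

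**What the plan says.** **The coach.** Under Resources Necessary for Human Research Protection, the Study Coordinator/Coach is to "be responsible for enrolling subjects, scheduling study visits, all aspects of data collection, entering study data into REDCap". The same paragraph has this person "contacting them on a weekly basis prior to surgery, educating and motivating them to engage in preoperative opioid reduction". The description of the intervention in Study Procedures, section 1, confirms the double role: a co-principal investigator will "train the study coordinator to effectively deliver this education within the CBT context employing MI techniques". The coaching goes to one arm only, since the Risks section says that "one-half of the subjects will be encouraged to gradually taper their opioid use in the month prior to surgery".

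**Knowledge of allocation.** Under Methods, section 3, the randomization scheme is "provided to the study coordinator who will assign consecutively enrolled subjects to group".

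**Pre-operative visit (T0).** Study Procedures, section 1, says that intervention patients "will meet with the study coordinator and baseline assessments will be repeated". Their interview about the programme takes place in the same session. That paragraph names no assessor for controls, although Study Design says that both groups give pre-operative data.

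**Follow-up.** Methods, section 6, says that "subjects will be contacted via telephone at 3- and 6-months following surgery to determine if CPSP is present". The caller is not named.

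**Other text on staff.** Data Management (Methods, section 5) gives data entry to research assistants and, further on, data collection to research staff in general. It also has the coordinator inspect completed datasets and supervise quality assurance.

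**Source of the data.** Study Procedures, section 2, takes everything except the 72-hour data directly from the patient, with the PDMP used to validate opioid use.

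**The concern.** BPI, PCS, PROMIS, the CPSP checklist and stated opioid dose all depend on what the patient chooses to report. An intervention patient may be giving those answers to the person who has spent four weeks encouraging coping and a lower opioid dose, and who knows the allocation. Controls have no such relationship with the assessor, whoever that is. A reporting shift of this kind would not cancel between arms. A larger sample would not remove it, and nothing in the Statistical Analysis section could detect or correct it.

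At stake is the trial's declared main purpose, which is reliable effect sizes for planning larger studies. A biased estimate would carry over into the design of the next trial.

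**Working it through.** **Step 1. Which outcomes are exposed?**

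| Outcome | How obtained | Independent check | Exposed? |
|---|---|---|---|
| BPI (primary), PCS, PROMIS | From the patient at baseline, T0, 3 and 6 months | None | Yes |
| CPSP checklist | Telephone, 3 and 6 months, caller unnamed | None | Yes, if the coach calls |
| Opioid use (MEDD) | Patient report | PDMP | Partly |
| 72-hour VAS | Ward scores every 4 hours, taken from the EHR, or a patient diary after early discharge | Recorded outside the coaching relationship | No |

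The PDMP check is itself described inconsistently. Study Instruments has it at every time point, but the schedule in Methods, section 4, shows it at baseline and follow-up only. T0 is the endpoint visit for Objective 2.

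**Step 2. Who assesses?** Resources gives all data collection to the coordinator/coach. Data Management gives collection to unspecified staff and entry to research assistants. Study Procedures names the coordinator at T0 for the intervention arm alone. These can be read as the coach assessing everyone, or as different assessors by arm. On the first reading, only one arm reports to its own coach. On the second, the assessor differs by arm. No section separates assessment from coaching.

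**Step 3. The plan's own effect figure.** The inputs, from Target Population and Accrual, are a baseline mean of 4.82, a pre-post improvement of 14.5%, an effect size of 0.33, 75 participants, 80% power and alpha 0.05 (taken as two-sided).

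- The stated n reproduces as a within-group paired test: with d = 0.33 and n = 75, the exact paired t-test has power 80.5%.
- Planned change: 0.145 × 4.82 = 0.70 points.
- Implied SD of change: 0.70 / 0.33 = 2.12 points.

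**Step 4. Illustration of size.** The documents give no bias figure. The shift b, in the coached arm only, is an assumption.

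- Share of the planned change: 0.2 / 0.70 = 29%; 0.4 / 0.70 = 57%.
- Suppose there is no true effect, 75 patients per arm and a between-arm comparison of change. Then SE = 2.12 × √(2/75) = 0.346.
- Two-sided rejection rate = 1 − Φ(1.96 − b/SE) + Φ(−1.96 − b/SE).

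| b (points) | b/SE | Rejection rate |
|---|---|---|
| 0 | 0 | 5.0% |
| 0.2 | 0.58 | 8.9% |
| 0.4 | 1.16 | 21.2% |

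The 0.70 is a pre-post change, while the bias would act between arms. It serves here only as a yardstick.

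**The case against.** **The documents do not show the coach collecting everything.** A reader might infer from the Resources paragraph that the coach personally collects every self-reported outcome in both arms. The text does not go that far. Being responsible for data collection in a staffing paragraph need not mean administering each form. Other sections mention other staff, the T0 assessor for controls and the follow-up caller are unnamed, and the 72-hour VAS comes from routine care or a diary. This stands and limits the point to an unspecified assessor and inconsistent text.

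**A safeguard exists for opioid use.** The PDMP check is real but partial, because the schedule leaves it out at T0. It does nothing for pain, distress or CPSP.

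**Direction and persistence are not shown.** A reader might infer that the bias must favour the intervention, and equally so at six months. The documents support neither. The scales have fixed items, the coordinator also consents all patients, an unblinded interviewer can influence either arm, and coaching contact is weekly only before surgery. What stands is that the coaching relationship exists in one arm.

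**The trial is a small pilot with exploratory contrasts.** This lowers the severity. It does not remove the point, because effect estimates are the stated product.

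**Study Design's claim of low risk of bias** justifies choosing randomization in general. It says nothing about assessors, so it should not be read as a false statement about them.

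**Conclusion.** The concern holds in limited form, as a should-fix. The role that coaches one arm and knows the allocation is also made responsible for data collection and is the named T0 assessor for that arm. No independent or blinded assessor is specified for the primary outcome or for the PCS, PROMIS, CPSP or self-reported opioid data, and the sections on data collection are inconsistent.

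This is a risk of bias in the between-arm estimates. It does not establish that bias will occur or that the effect estimates will be unreliable. Its size cannot be taken from the documents. The figures of 29% to 57% of the planned change, and of a 5% error rate rising to about 9% to 21%, rest wholly on an assumed one-arm shift of 0.2 to 0.4 points. The error rates also assume an SD of 2.12 in both arms.

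**What to change.** 1. Reconcile Methods sections 3 to 6, the pre-operative session in Study Procedures and the coordinator paragraph in Resources, so that one statement says who collects what, in each arm and at each visit. Settle in the same edit whether the PDMP is reviewed at T0.
2. State that patients in both arms self-complete the BPI, PCS, PROMIS, opioid-use items and CPSP checklist in the same way: on paper or a REDCap form at T0, and by REDCap link at 3 and 6 months. The coach neither administers the forms nor sees answers during completion. Keep the safety review of depression scores already described under Data and Safety Monitoring.
3. At T0, hold the satisfaction interview only after the outcome forms are complete.
4. Where a call is needed for non-completion, use an existing staff member other than the coach, if capacity is confirmed. That person should not conduct the satisfaction interview. Only intervention patients have it, so it would reveal the allocation.

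**Cost.** REDCap is in place and email addresses are already collected for follow-up, so self-completion needs mainly protocol wording and a survey link. A separate caller is less certain, because the Resources section itemises no research-assistant effort. Expect reminder calls and some online non-completion, given an expected mean age of 67. Patients still know their arm, so some reporting bias would remain. The change removes only the part tied to answering one's own coach.

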The research will be conducted in the Department of Orthopaedic Surgery at Penn Presbyterian Medical Center, and data analysis will be performed at the Biostatistics * Evaluation * Collaboration * Consultation * Analysis (BECCA) lab at the U Penn School of Nursing.

The duration of subject participation is approximately seven (7) months beginning four (4) weeks prior to surgery and ending following the 6-month data collection time point. The baseline study session will last approximately 30minutes for those in the control group and 60minutes for those in the experimental group. For those in the experimental group, subjects will spend approximately nine (9) hours prior to surgery receiving the intervention. For those in the control group, subjects will spend approximately four (4) hours prior to surgery receiving the standard educational care. Just prior to the surgery, subjects in both groups spend approximately 45minutes providing pre-operative data, and they will additionally spend one (1) hour providing data at the 3- and 6-month follow up at 30minutes each. Thus, the duration of participation for those in the experimental group is approximately 12 hours, and for those in the control group, approximately 7.5 hours.

METHODS:

1. Study Instruments:

Preoperative chronic pain – The severity of preoperative chronic pain will be evaluated with the Brief Pain Inventory (BPI),⁵² along two dimensions: intensity and interference. Pain intensity is rated on a 0 (no pain) to 10 (worst pain imaginable) scale as the worst in the past 24 hours, least in the past 24 hours, average pain and current pain. Pain interference is measured in 7 areas: general activity, mood, walking ability, work, sleep, enjoyment of life and relationships on a 0 (no interference) to 10 (interferes completely) scale. The composite mean of these scores are used as a pain interference score. BPI scores will be collected prior to the intervention and compared to those collected just prior to surgery and at 3- and 6-month follow-up.

Long-term opioid use – Preoperative opioid use will be measured by converting to morphine equivalent daily dose (MEDD) prior to beginning the intervention, during the study visit just prior to surgery and at the 3 and 6 months follow up if the patients are still taking opioids. At each timepoint, state prescription drug monitoring program will be queried as a check on self-reported opioid use.

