Following each DSMB meeting, the designated member standing in for the Chair will make recommendations to Drs. [name] and [name] and a final report (edited by all Board members not in conflict with this project) will be prepared and submitted to NINR, the Penn IRB, and the FDA (if required) according to each body's reporting requirements. In addition, a Data Safety Monitoring Board report is issued to the NINR Project Officer with the annual progress report.

The DSMB will meet to review safety data every six months (unless more frequent meetings are deemed necessary). At least two weeks prior to each meeting, the investigative team will submit to the DSMB a DSMB Report detailing screening activities; reasons for screening failures; subject enrollment (actual vs. expected); sociodemographic characteristics of enrolled subjects; and subject disposition (including reasons for attrition). In addition, the number and nature (severity and relatedness to study procedures) of all adverse events will be described. Finally, a random or purposive sample (depending on DSMB request) of subject case report forms (CRFs) will be submitted with the DSMB Report, to enable assessment of compliance with IRB requirements, conformance with informed consent requirements, verification of source documents and investigator compliance.

In the event that a subject scores high on the depression scale, a licensed clinical psychologist (co-PI [name]) will be available to assess immediately any patient who exhibits extreme anxiety, depression or suicidal ideation on routine screening or during the preoperative period. All research and clinical staff will call his cell phone when a patient with significant anxiety, depression or suicidal ideation is encountered. All patients who acknowledge extreme anxiety, depression or suicidal ideation and intent will be contacted immediately by [name] and an appropriate treatment plan will be enacted.

8. Investigator's Risk/Benefit Assessment:

Based on the characteristics of the risks associated with study participation, and efforts in place to minimize these risks, the risks to subjects are considered reasonable in relation to the anticipated benefits to research participants and others.

INFORMED CONSENT:

1. Consent Process:

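### Between baseline and the pre-operative visit, adverse events and distress episodes are likely to be ascertained more completely in the intervention arm, because only that arm has scheduled coach contact and no common elicitation method is specified.

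*Combined protocol and SAP*

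**What the plan says.** **Intervention arm.** The Study Coordinator/Coach paragraph (Resources Necessary for Human Research Protection) describes the coach as "contacting them on a weekly basis prior to surgery, educating and motivating them to engage in preoperative opioid reduction". That paragraph does not name an arm, but Risks (Opioid taper) does: "As a part of the intervention and with the guidance of their trained coach, one-half of the subjects will be encouraged to gradually taper". The same section adds that "subjects will be instructed to contact their coach should the symptoms become severe".

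**Control arm.** Treatment as usual is a "mandatory 4-hour education class delivered by a nurse educator or physical therapist". The data collection schedule (Methods, section 4) has no column between Baseline (T-4 weeks) and T0.

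**Both arms.** Study Design states: "Just prior to the surgery, subjects in both groups spend approximately 45minutes providing pre-operative data". The schedule lists the PROMIS measures at baseline and T0 without limiting them to one arm. However, the paragraph on the pre-operative session (Study Procedures, section 1) names only the experimental group.

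**Events.** Risks (Acute Anxiety or Depressive Symptoms) expects that "the opioid taper for the intervention group, or the upcoming surgery for both groups may precipitate unanticipated symptoms of acute anxiety or depression". Under Data and Safety Monitoring, "All research and clinical staff will call his cell phone when a patient with significant anxiety, depression or suicidal ideation is encountered", and the report to the board is one in which "the number and nature (severity and relatedness to study procedures) of all adverse events will be described". Study Instruments (Potential confounders) names only events after surgery for entry in the study database. No section says how or when pre-operative events are to be elicited.

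**The concern.** The plan expects distress before surgery in both arms: from the taper in one, and from the coming operation in both. The control rate is the within-trial benchmark for separating the two sources. If an episode that starts and resolves between baseline and T0 is more likely to come to notice in the coached arm, equal true rates will tend to appear as an excess there.

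Three things could be affected:

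- The board's view of harm. It receives event counts with severity and relatedness, and its remit includes stopping a study for risk.
- Withdrawals for safety, which Early Withdrawal of Subjects links to extreme anxiety or depression.
- Referral to the study psychologist, which depends on staff meeting the patient. Unequal referral would be an unequal co-treatment for the depression and anxiety comparison in Objective 2. The documents give no referral rate, so this is a possibility and no more.

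**Working it through.** The plan states no figure on this point, so there is none to reproduce.

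**Step 1. Count study contacts after baseline, up to and including T0.**
- Intervention: weekly for 4 weeks plus T0, so 4 if the last weekly contact coincides with T0 and 5 if it does not.
- Control: 1 (T0). If the paragraph on the pre-operative session were followed literally, it would be 0.

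**Step 2. Look for an unlisted control contact in the participation hours (Study Design).**
- Experimental: 1 + 9 + 0.75 + 1 = 11.75 h, against about 12 stated.
- Control: 0.5 + 4 + 0.75 + 1 = 6.25 h, against about 7.5 stated.
- The remaining 7.5 − 6.25 = 1.25 h is not itemised, and no section assigns it to a study contact.

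**Step 3. Illustrate by event duration.** Assumptions, none of them in the documents: onset is uniform over 28 days, contacts fall on days 7, 14, 21 and 28 (intervention) or day 28 only (control), an event present at a contact is always found, and true rates are equal. For an event lasting d days, detection is min(1, d/7) in the intervention arm and d/28 in controls.
- d = 7: 1.00 v 0.25, ratio 4.0
- d = 14: 1.00 v 0.50, ratio 2.0
- d = 21: 1.00 v 0.75, ratio 1.3

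Now let the T0 visit recover a share r of resolved events. Control detection becomes d/28 + (1 − d/28)r. For d = 7 and r = 0.5 this is 0.25 + 0.75 × 0.5 = 0.625, and the ratio falls to 1/0.625 = 1.6.

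The chance of a spurious excess in the intervention arm (two-sided Fisher test, p < 0.05, 75 per arm) is:

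| True rate, both arms | Duration | r = 0 | r = 0.5 | r = 0.75 |
|---|---|---|---|---|
| 20% | 7 days | 0.76 | 0.17 | 0.06 |
| 20% | 14 days | 0.32 | 0.08 | 0.04 |
| 10% | 7 days | 0.34 | 0.08 | 0.03 |
| 5% | 7 days | 0.08 | 0.02 | 0.01 |

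**Step 4. Illustrate by detection per contact.** Suppose each contact finds an event with probability q. Detection is 1 − (1 − q)^k, with k = 4 to 5 in the intervention arm and k = 1 in controls. The last column uses a true rate of 20% in both arms, 75 per arm and a normal-approximation test.

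| q | Intervention | Control | Ratio | Chance of spurious excess |
|---|---|---|---|---|
| 0.2 | 0.59–0.67 | 0.20 | 3.0–3.4 | 0.42–0.54 |
| 0.5 | 0.94–0.97 | 0.50 | 1.9 | 0.33–0.37 |
| 0.9 | 1.00 | 0.90 | 1.1 | 0.05 |

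If onset is spread evenly over the four weeks (k = 4, 3, 2 or 1 remaining contacts, averaged), the ratios fall to 2.1, 1.5 and 1.1.

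**Reading.** In both models, equal true rates give an apparent excess in the intervention arm. Its size depends almost wholly on inputs that the plan does not give.

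**The case against.** The strongest reply is that several routes cover both arms. PROMIS is scheduled at T0 without arm restriction, and a high depression score itself prompts assessment. All research and clinical staff are to escalate distress. Data Management provides weekly reports that include health events. A primary study clinician handles health problems during participation. Controls also meet clinical staff at the class. All this stands, and the models in the working give these routes no credit outside T0. None of them, however, is a scheduled query put to both arms, and a T0 score does not recover an episode that has already resolved or an event unrelated to mood.

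It is also fair to say that coach contacts are described as education and motivation, with no instruction to ask about or record adverse events. The coaching does cover recognising and managing withdrawal symptoms, so symptoms will be discussed, but perfect detection by the coach is an upper bound.

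The plan contains no between-arm test of harms and does not say that the board sees counts by arm. Harm comparison is not a study objective. The probabilities of a spurious excess therefore belong to a hypothetical analysis.

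Finally, closer contact with patients who are tapering is part of delivering the intervention and safeguarding them. That stands too. The point concerns which events are compared between arms, and gives no reason to reduce coach contact.

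**Conclusion.** The concern holds in a limited form. Ascertainment between baseline and T0 is likely to be more complete in the intervention arm, because only that arm has scheduled contact and a dedicated reporting route, and no common elicitation method is specified. This rests on two readings: that weekly contact belongs to the coached half of the sample, as Risks (Opioid taper) indicates, and that the schedule is complete in showing no control contact in the window.

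A reader might infer that pre-operative events will be found mainly in one arm, or that a falsely significant excess is probable (0.76 in the most extreme case shown). The documents do not support either. That figure needs 7-day events, a 20% true rate, perfect detection by the coach, no recall at T0 and a test that the plan does not contain. It falls to 0.17 with 50% recall, or to 0.08 at a 5% true rate. Nor are the PROMIS comparisons at T0 themselves compromised by coach contact. An effect through unequal psychologist referral is possible but unquantified.

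Severity is minor: the bias would tend to overstate harm in the intervention arm, and the remedy is cheap. It needs to be in place before enrolment, because control events that are never asked about may not be recoverable later.

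**What to change.** 1. Add one identical structured adverse-event and distress query to the T0 session in both arms, covering the whole period since baseline. Enter those pre-operative events in the study database as well as the post-surgical ones.
2. Reconcile the paragraph on the pre-operative session, which names only the experimental group, with Study Design and the schedule, so that controls receive the query. Clarify the 1.25 h of control time that is not itemised.
3. Record the source of each event: common visit query, coach contact or spontaneous report.
4. State that any between-arm harm comparison, whether shown to the board or reported, uses events from the visits common to both arms. List coach-elicited events separately, and continue to act on them for safety.
5. Log study-psychologist assessments by arm and report the counts beside the depression and anxiety results.

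**Cost.** A few minutes at an existing visit, one REDCap form and a change of table layout, with no extra staff, visits or patients. The downside is about four weeks of recall. Recall may be somewhat better in the intervention arm, whose patients are taught to recognise withdrawal symptoms, so the query narrows the imbalance without being certain to remove it.
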